#### **Rationale:**

Approximately one-third of WWE have catamenial epilepsy, or cyclic seizure exacerbations in relation to the menstrual cycle. In women with ovulatory cycles, catamenial seizure exacerbations can occur either during the perimenstrual (catamenial 1, C1) or the preovulatory (catamenial 2, C2) phases of the menstrual cycle (Herzog et al., 1997; Herzog 2008).

C1 seizure exacerbations are thought be related to the rapid premenstrual withdrawal of progesterone (Herzog 2008) (Figure 1). Progesterone has been found to have dual actions on the brain. First, the progesterone neurosteroid metabolite allopregnanolone exerts an anticonvulsant effect by binding to the gamma-amino-butyric acid (GABA) type A receptor to enhance GABA action (Herzog et al., 1997; Joshi at al., 2013). The rapid withdrawal of allopregnanolone premenstrually may impair GABAergic inhibition and therefore precipitate seizures. Second, progesterone has recently also been found to exert a proconvulsant effect. Shiono et al. (2019) found that progesterone receptor activation increased seizure frequency in epileptic animals. Joshi et al. (2018) discovered that progesterone receptor activation increased excitatory transmission by upregulating a-amino-3-hydroxy-5-methyl-4-isoxazole propionic acid (AMPA) receptor GluA1 and GluA2 subunit expression in the rat model. The use of a progesterone and glucocorticoid receptor blocker then attenuated neurosteroid withdrawal seizures.

C2 seizure exacerbations, alternatively, may be secondary to the preovulatory estrogen surge (Figure 1). In the animal model, estradiol has been found to act as proconvulsant by potentiating excitatory synaptic transmission by increasing the probability of glutamate release; this may be enhanced via AMPA mediated conductance (Smith, 1989; Smejkalova and Woolley, 2010). Estradiol has also been found to increase neuronal metabolism and discharge rates (Smith, 1989; Hardy, 1970).

Harden C and Pennell P. (2013). Neuroendocrine considerations in the treatment of men and women with epilepsy. The Lancet Neurology. 12 (1): 72-83.

**Figure 1**. Illustration of how fluctuations in progesterone and estradiol concentration contribute to perimenstrual (catamenial 1, C1) and preovulatory (catamenial 2, C2) cyclic seizure exacerbations.

The role of hormonal treatment of catamenial epilepsy was previously investigated in the NIH Progesterone Trial, a randomized, double-blinded clinical trial of progesterone versus placebo therapy in the treatment of intractable focal seizures in ovulatory women with and without catamenial epilepsy (Herzog et al., 2012). The principal outcomes were the proportion of  $\geq$ 50% responders and the change in seizure frequency between the 3-month baseline and 3-month treatment phases. Unfortunately, no significant differences were found between progesterone and placebo therapy, though women with both C1 and C2 seizure exacerbations were included in the catamenial arm. Of note, on post hoc analysis, women with high levels of perimenstrual seizure exacerbation were found to be responsive.

Apart from trial design issues (the level of catameniality may have been insufficient for inclusion in the catamenial arm and women with C2 seizure exacerbations were also in the catamenial arm), the lack of effectiveness of progesterone suggests that the anticonvulsant effects of progesterone alone are insufficient in preventing catamenial seizure exacerbations. As previously described by Joshi et al. (2018), progesterone receptor activation may contribute to excitotoxicity by increasing AMPA receptor mediated glutamatergic transmission. The rapid withdrawal of allopregnanolone may therefore provoke seizures by disrupting the homeostatic balance of excitatory and inhibitory regulation, as in vivo and in vitro studies suggest that central neurons regulate excitatory and inhibitory balance slowly, over hours to days (Turrigiano 2011). Therefore, limiting the excitotoxicity of progesterone receptor activation may be particularly efficacious in treating perimenstrual catamenial seizure exacerbations.

The purpose of the proposed investigation is to carry out a pilot study of add-on perampanel (Fycompa) in women with perimenstrual (C1) catamenial epilepsy. Perampanel, a noncompetitive AMPA receptor antagonist, is uniquely positioned to decrease progesterone receptor mediated excitotoxicity. This mechanism of action would allow a novel use of perampanel as an effective treatment of C1 catamenial epilepsy.

Of note: Future studies should investigate the use of perampanel in women with preovulatory (C2) catamenial epilepsy, as estradiol's proconvulsant effect is potentially being mediated through the enhancement of AMPA. This population is not included in this study. Women in clinic typically report clustering of seizures specifically around their menses (perimenstrual) so I chose to target this population (C1 pattern) first as I find this more clinically relevant.

#### **Study Design:**

This is an unblinded pilot study enrolling women with C1 catamenial focal epilepsy. Subjects will chart menses and seizures for a 2 month baseline period and then be randomized into 2 parallel arms: (1) Fycompa 4 mg daily and (2) Fycompa 4 mg daily to be increased to 6 mg daily peri-menstrually (Day -7 until Day 4 of menstruation where Day 1 is the first day of menstrual flow). During this treatment phase, subjects will continue to chart menses and seizures. Other anticonvulsant medication doses will not be changed during the baseline or treatment study period.

#### **Objectives:**

*Primary*: To determine the responder rate in each group (percent of patients experiencing a 50% or greater reduction in seizures) relative to baseline seizure frequencies.

Secondary: Changes in seizure frequency in each group relative to baseline seizure frequencies.

Tertiary: Comparisons of primary and secondary outcomes between two groups.

# **Study Schema:**

#### **Subjects and Centers:**

This a single site study at a tertiary care academic center, the University of Florida at Jacksonville. 50 total female subjects will be enrolled.

#### **Inclusion Criteria:**

- 1. Female
- 2. Diagnosis of focal onset seizures (FOS)
  - i. Established by clinical history and an EEG
  - ii. Patients with a normal EEG may be included if they met other diagnostic criteria based on clinical history
- 3. Presumably ovulatory women based on menstrual cycles of 21-35 days from beginning of menstrual flow to the beginning of the next menses
- 4.  $\geq$ 18-50 years old
- 5. ≥2 unprovoked seizures per month despite drug trials with ≥1 first-line antiepileptic drugs (AED)
- 6. Seizures must show a C1 catamenial pattern in 2 of 3 documented cycles
  - i. C1 pattern will be defined as a two-fold increase in average daily seizure frequency during the menstrual phase, as compared to the follicular and luteal phases of the ovulation cycle, in 2 of 3 documented cycles. The menstrual phase will be defined as days -3 to +3 of the menstrual cycle (where onset of menstruation is defined as day 1) (Herzog et al, 1997). Of note, in the NIH Progesterone Trial, the level of catameniality was 1.69 based on Herzog et al. (1997) criteria though this trial will use a level of 2 to include women only with high levels of perimenstrual catamenial exacerbation.
- 7. Willingness and ability to comply with scheduled visits and study procedures

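### Does the C1 entry rule need changing because it is silent on preovulatory days and on women who show both C1 and C2 patterns?

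*Protocol*

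**What the plan says.** The Protocol's Rationale says that exacerbations in ovulatory cycles fall either in the perimenstrual phase (C1) "or the preovulatory (catamenial 2, C2) phases of the menstrual cycle". Of the earlier progesterone trial it says that "women with both C1 and C2 seizure exacerbations were included in the catamenial arm", and it names this among that trial's design issues: "women with C2 seizure exacerbations were also in the catamenial arm". It then says "Future studies should investigate the use of perampanel in women with preovulatory (C2) catamenial epilepsy" and adds "This population is not included in this study". The reason given is that clinic patients typically describe clustering around menses, so the C1 group is studied first.

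Inclusion Criterion 6 puts this into practice: "Seizures must show a C1 catamenial pattern in 2 of 3 documented cycles". Item 6.i asks for a two-fold rise in average daily seizure frequency in the menstrual phase, "as compared to the follicular and luteal phases of the ovulation cycle". Only one phase receives days: "The menstrual phase will be defined as days -3 to +3 of the menstrual cycle". A published source is cited there. The next sentence says the earlier trial reached a level of 1.69 on that source's criteria and that this trial uses 2.

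None of the five exclusion criteria mentions a C2 or mixed pattern. The SAP does not touch the point.

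**The concern.** Two things look wrong. First, the Rationale says C2 women are out and treats their presence in the earlier trial as a fault, yet a woman who meets C1 and also clusters before ovulation breaks no criterion. Second, criterion 6 does not settle how her calendar is scored. Preovulatory days may sit inside the follicular phase or be left out as a phase of their own. The two comparison phases may be pooled, or each may have to be exceeded.

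The stake is the contrast between arms. The arms differ only from Day -7 to Day 4, while the responder outcome counts every seizure. A woman with a second cluster elsewhere has a smaller share of her seizures on the days when the arms differ, so she would shrink the arm difference. The pilot is meant to supply the data for the next trial's sample size, and that trial would need an entry rule it can reproduce.

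**Working it through.** The documents state no figure on this point, so there is none to reproduce. The checks below ask how much the silence can matter.

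**Inputs.** From the Protocol: menstrual window of days -3 to +3, which is 6 days with no day 0; threshold 2, in 2 of 3 cycles; treatment window Day -7 to Day 4, counted as 11 days in the drug-supply section, so 6 menstrual days plus 5 others. Assumed: a 28-day cycle (the Protocol allows 21 to 35), leaving 22 non-menstrual days; k = 5 to 9 preovulatory days, outside the treatment window; C2 ratio c = 2 to 3; Poisson counts averaging 2 to 8 per cycle. Rates are relative to ordinary days; a is the menstrual rate.

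**1. Can the reading change eligibility?** Take 3 seizures in the 6 menstrual days, 4 in 7 preovulatory days and 2 in the other 15.
- Preovulatory days counted: (3/6)/(6/22) = 1.83, not C1.
- Left out: (3/6)/(2/15) = 3.75, C1.

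So it can. The example is a marked one, though: its preovulatory rate, 4/7 = 0.57 per day, exceeds its menstrual rate of 0.50.

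**2. Chance of entry.** If p is the chance that one cycle passes, the chance of at least 2 of 3 is 3p²(1-p) + p³. With pooled phases, k = 7 and a mean of 4 seizures per cycle:

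| Woman (true ratios) | Preovulatory days counted | Left out |
|---|---|---|
| Both patterns (3 and 3) | 36% | 65% |
| C2-only (3) | 4% | 20% |
| C1-only (3) | 63% | 71% |

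Over means of 2 to 8 and k of 5 to 9, C2-only women enter 1% to 6% of the time if the days are counted and 11% to 25% if left out. If each of two 11-day phases must be exceeded, the C1-only woman passes 35% of the time.

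**3. Size of the dilution.** The share of seizures on Day -7 to Day 4 is (6a + 5)/(6a + S), where S = 22 + k(c - 1).
- C1-only (S = 22): a = 2 gives 17/34 = 50%; a = 3 gives 23/40 = 57.5%.
- Both patterns at 3 and 3, k = 7 (S = 36): 23/54 = 43%. Her pooled ratio is 3/(36/22) = 1.83, below 2.
- Both patterns, C1 2 and C2 3, k = 9 (S = 40): 17/52 = 33%. Her pooled ratio is 2/(40/22) = 1.10.

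The last two women do not truly meet a pooled rule that counts preovulatory days. For women who do, set the pooled ratio R to 2 or 3, so that a = R × S/22:
- R = 2, k = 9, c = 3: a = 3.64, share 26.8/61.8 = 43%.
- R = 2, k = 5, c = 2: a = 2.45, share 19.7/41.7 = 47%.
- R = 3, k = 9, c = 3: a = 5.45, share 37.7/72.7 = 52%.
- R = 3, k = 5, c = 2: a = 3.68, share 27.1/49.1 = 55%.

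That is 43% to 47% against 50% at R = 2, and 52% to 55% against 57.5% at R = 3: a drop of about 2 to 7 percentage points.

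**4. What a C2 exclusion would do.** Apply a two-fold preovulatory rule in 2 of 3 cycles to women who passed the pooled C1 rule (true ratios of 3, k = 7; 400,000 simulated women per cell):

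| Mean seizures per cycle | 2 | 4 | 8 |
|---|---|---|---|
| Versus all other days: C1-only wrongly removed | 5% | 4% | 1% |
| Versus all other days: both-pattern caught | 24% | 31% | 31% |
| Versus other non-menstrual days: C1-only wrongly removed | 13% | 24% | 21% |
| Versus other non-menstrual days: both-pattern caught | 41% | 68% | 80% |

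The gentle rule misses 69% to 76% of the women it is aimed at. The sharper one discards 13% to 24% of the intended population.

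**The case for a change.** The strongest case for acting is that the Rationale names C2 women in the earlier trial as a fault, so the investigator evidently regards keeping them out as an improvement, and nothing in the criteria completes that. Two members of staff could score one calendar differently. If preovulatory days are left out, the women with shares of 43% and 33% above do truly qualify, and the dilution is then larger. The SAP also analyses the responder rate by chi-square, which suggests a comparison of arms. Clarifying the wording would cost almost nothing.

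Much of this stands as description. The phase days and the pooling rule are unstated, and mixed-pattern women are not mentioned. It does not amount to a contradiction. The Rationale sets C1 women against C2 women and picks the former. Its remark on the earlier trial can mean that both kinds of women were enrolled, and requiring C1 answers that. Criterion 6 names three phases, so the plain reading is that follicular and luteal days are the rest of the cycle, preovulatory days included. It also presents its rule as cited criteria with the level raised to 2. Whether that source gives the other days cannot be checked here.

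**Conclusion.** No change to the plan is needed. This is missing detail that the site can fill sensibly by fixing one scoring convention for all calendars. The primary objective, the responder rate within each group of C1 women, stays interpretable on any of the readings. The Objectives place the comparison of groups third, randomisation keeps it fair, and a later trial using the same criterion scored the same way would enrol the same mix.

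On the plain pooled reading the dilution is about 2 to 7 percentage points in the share of seizures on Day -7 to Day 4, for each woman with both patterns. It is larger if preovulatory days are left out. The documents do not say how many C1 women also show C2, so the total effect among the 50 is unknown. The one substantive remedy, a C2 exclusion, is a debatable trade-off rather than a correction: it either misses most of its target or costs a small pilot a material share of eligible women.

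These sizes rest on the assumed 28-day cycle, the 5 to 9 preovulatory days, C2 ratios of 2 to 3 and Poisson counts. The judgement that this is a gap in wording rests on the text alone.

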# **Exclusion Criteria:**

Version 3.0, March 17, 2022

- 1. Progressive neurologic or systemic disorder
- 2. Use of systemic hormonal contraception during 3 months prior to enrollment (however, subjects with a progestin-releasing IUD who still have monthly periods may be enrolled)
  - a. Women on system hormonal contraception will be excluded as these women are not ovulatory
- 3. Subject is pregnant or breastfeeding
- 4. Active suicidal or homicidal ideation
- 5. Decisionally impaired or C-comatose individuals.

#### Other Therapy: N/A

#### **Efficacy Measures:**

- 1. Primary: To determine the responder rate (percent of patients experiencing a 50% or greater reduction in seizures) relative to baseline seizure frequencies.
- 2. Secondary: Changes in seizure frequency relative to baseline seizure frequencies.
- 3. Tertiary: Comparisons of primary and secondary outcomes between two groups.

#### **Safety Measures:**

- 1. We do not plan to have an internal Data Safety Monitoring Board. PI and study coordinator to be in charge of safety measures.
- 2. There will be a baseline Columbia-Suicide Severity Rating Scale (C-SSRS) at enrollment to screen for suicidal ideation and behaviors. If suicidal ideation or behaviors are present, subjects will not be enrolled in the study. At each followup visit, we will screen for changes in this scale. During each telephone call, we will screen for depressive symptoms and suicidality by asking patients if they are suicidal.
  - 1. Suicidality plan:
    - a. C-SSRS will be performed at each visit by study coordinator. Study coordinator to contact PI if there is a change in the C-SSRS.
    - b. For suicidal ideation and/or behaviors, we will refer subject to the Emergency Department for emergent evaluation and treatment. Phone number for suicide hotline will also be provided. Will also discontinue enrollment in trial and study drug.
- 3. We will screen for behavioral changes at each visit and during each telephone call.
  - 1. Will screen by asking specifically if patient is having:
    - a. Thoughts of harming others, physical assault, or threating behavior
    - b. Worsening anger, aggression, or irritability

- 2. If thoughts of harming others, physical assault, or threating behavior develops in a subject, will discontinue enrollment in trial and study drug. Subject will be referred to the Emergency Department.
- 3. If worsening anger, aggression, or irritability is mild or moderate, will continue enrollment and continue monitoring subject.
- 4. If worsening anger, aggression, or irritability is severe, will discontinue enrollment in trial and study drug.
- 4. We will check a serum pregnancy prior to enrollment in baseline phase and then a urine pregnancy test prior to enrollment in treatment phase to ensure pregnant women are excluded.
- 5. Subjects who are not status post tubal ligation or who do not have an IUD must agree to use a double barrier contraceptive method while enrolled in study (e.g. condom + spermicide OR condom + diaphragm/cervical cap).
  - a. During monthly telephone calls while enrolled in the study (see "Data Collection" below), subjects will be reminded to utilize the double barrier contraceptive method while enrolled in the study.

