# **Adverse Events:**

- 1. Serious FDA definition: A serious adverse event results in death, is lifethreatening, requires inpatient hospitalization or prolongation of existing hospitalization, results in persistent or significant disability / incapacity, results in a congenital anomaly / birth defect.
- 2. Severity: Severity describes the intensity of a specific event and will be graded as:
  - a. Mild: easily tolerated, causing minimal discomfort.
  - b. Moderate: sufficiently discomforting to interfere with every day activities.
  - c. Severe: prevents normal every day activities.
- 3. Relationship will be detailed as:
  - a. Unrelated: There is no association between the study intervention and the reported event.
  - b. Related: A definite causal relationship exists between the event and the study, and other conditions (concurrent illness, progression of disease or concomitant medication use do not appear to explain the event).
  - c. Cannot be ruled out: The event might be related to the intervention, but could also have been produced by other factors.

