# **Correlative Science:** N/A

# **Statistical Analysis:** The primary outcome (50% responder rate) will be analyzed using Chi square analysis. The secondary outcome, changes in seizure frequency from baseline to treatment, will be analyzed using paired t-test or ANCOVA.

The pilot should provide data for calculation of the required sample size for demonstration of a significant difference or equivalence between the two groups with 80% power.

Data Collection:	Subjects will be seen in the clinical trial clinic for three separate visits. Subjects will be seen at enrollment and then also after the completion of baseline (first 2 months of charting) and treatment phases (second 2 months of charting). Subjects will also be contacted by phone on a monthly basis to verify compliance with charting and treatment and to monitor for any adverse effects. [Subjects will also be reminded to utilize double barrier contraceptive methods during these phone calls]. Data will be obtained via paper charting on printed calendar and then entered into an electronic database (REDCap) for analysis. All adverse events will be reported to the IRB.
Study Drug Regimens:	During the treatment phase, subjects will be randomized into 2 parallel arms: (1) Fycompa 4 mg daily and (2) Fycompa 4 mg daily to be increased to 6 mg (4-mg pill and 2 mg pill) daily peri-menstrually (from Day -7 until Day 4 of menstruation where Day 1 is the first day of menstrual flow). This treatment phase will last for two menstrual cycles.
Study Drug Requested Per Patient:	Group 1 (n=25), to take 4 mg daily for 2 menstrual cycles or 60 days, 1500 tablets (25 subjects x 60 days).
	Group 2 (n=25), to take 4 mg daily (1 tablet) with 6 mg daily (1 4-mg tablet and 1 2-mg tablet) for 11 days around menses for 60 days. This would be 1500 tablets (25 subjects x 60 days) of 4 mg tablets and 550 tablets (25 subject x 22 days) of 2 mg tablets.

Are Clinical/Drug Supplies Requested? (check only 1 box): D YES' ('YES') 'NO'

Total study drug amount in units (tablets, capsules, vials, etc.):		
Total Active Drug	3000 tablets of 4 mg tablets needed	
	550 tablets of 2 mg tablets needed	
Amount of Pure Substance		
(if applicable)		

Estimated Length of Enrollment:

I plan to enroll 50 patients within a 6 month time period.

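### The monthly calls are meant to screen for depressive symptoms, but the only stated method is a question about suicidality

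*Protocol*

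**What the plan says.** Safety Measures, item 2, sets the content of the mood-related part of each call: "During each telephone call, we will screen for depressive symptoms and suicidality by asking patients if they are suicidal". The visit instrument is introduced in the same item: "There will be a baseline Columbia-Suicide Severity Rating Scale (C-SSRS) at enrollment to screen for suicidal ideation and behaviors". It is repeated at each visit, and the escalation rule is "Study coordinator to contact PI if there is a change in the C-SSRS". The action plan that follows deals with suicidal ideation and behavior only.

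Item 3 lists further questions for calls and visits. They cover harm or threats to other people, and "Worsening anger, aggression, or irritability". Each has a stated response.

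Item 5a shows that calls run through the whole of participation: "During monthly telephone calls while enrolled in the study". They therefore also take place in the drug-free baseline.

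The Data Collection text adds a general inquiry. Subjects are "contacted by phone on a monthly basis to verify compliance with charting and treatment and to monitor for any adverse effects", and "All adverse events will be reported to the IRB". The Adverse Events section supplies the grading: "Severity describes the intensity of a specific event and will be graded as" mild, moderate or severe.

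The SAP does not address this point.

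**The concern.** Item 2 announces a screen for two things and describes how to do one of them. A coordinator who follows the sentence asks whether the woman is suicidal, hears no, and records a negative screen for depressive symptoms that were never asked about.

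This matters because there are only three visits: at enrollment, after baseline and after treatment. Between the visits that open and close treatment, the calls are the only scheduled contact. The protocol plans no internal safety board and leaves safety to the investigator and the coordinator. The one mood-related question on the call turns positive only at the point where the plan already requires emergency referral and stopping the drug. Low mood short of that has no prompt of its own, and grading and IRB reporting begin only once the symptom has come to light.

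**Working it through.** **Targets against methods.** The plan states no figure to reproduce here, so the check starts with the text.

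| Procedure | When | What it asks about | Asks about low mood? |
|---|---|---|---|
| Item 2, call question | Each call | Being suicidal | No |
| Item 2, C-SSRS | Each visit | Described as suicidal ideation and behaviors | No |
| Item 3, behavioral questions | Each call and visit | Harm or threats to others; anger, aggression, irritability | No (irritability overlaps slightly but is listed as a behavioral change) |
| Data Collection, general inquiry | Monthly calls | Any adverse effect, wording not given | Not specifically |

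No row contains a targeted question on low mood or loss of interest, and no action step addresses depressive symptoms without suicidality. Item 3 shows how the protocol writes a targeted screen when it wants one: it names the symptoms and gives a response. Item 2 does not do this for depressive symptoms.

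**How many calls are affected.** Inputs:
- 50 women (Subjects and Centers).
- Cycle length 21 to 35 days (Inclusion Criteria, item 3).
- Treatment of two cycles, costed at 60 days (Study Drug Requested Per Patient).
- Baseline of 2 months, taken as about 60 days.
- Assumption: calls at 30-day spacing, counted only when strictly between visits. The protocol says monthly and does not fix the days.

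On-drug calls per woman:
- Shortest treatment, 2 × 21 = 42 days: day 30, so 1 call.
- Drug-supply figure, 60 days: day 30, so 1 call.
- Longest treatment, 2 × 35 = 70 days: days 30 and 60, so 2 calls.

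A second on-drug call needs more than 60 days of treatment, that is, an average cycle above 60 / 2 = 30 days.

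Totals:
- On-drug calls: 50 × 1 = 50; ceiling 50 × 2 = 100.
- Baseline calls: 50 × 1 = 50.
- All calls: 50 + 50 = 100; ceiling 100 + 50 = 150.

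**The case against.** The strongest reply is that little risk is left uncovered. Suicidality, the gravest outcome, is asked about at every call and measured at every visit, with a clear action plan. Hostility and irritability have their own questions. The same monthly calls monitor for any adverse effect, and the protocol does not say that this is limited to what a woman volunteers. The documents give no depression rate and do not describe depression as a risk of the drug. On this view the point is one loosely worded clause in a 50-woman pilot, and deleting the reference to depressive symptoms would also remove the mismatch.

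Much of this stands as a limit on the size of the point. Monitoring is not absent, and whether the general inquiry would draw out low mood depends on how it is asked, which the protocol does not say. Half of the 100 calls fall before any drug is given, so the figure that bears on drug-related low mood is about 50. The ceiling of 100 on-drug calls is remote: every woman would need more than 60 days of treatment, while the 4 mg supply requested is 50 × 60 = 3000 tablets.

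It does not remove the defect. The protocol itself chose to screen for depressive symptoms, and the method it gives cannot do so. Deletion would make the sentence consistent only by dropping a safety aim that the sponsor wrote down.

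**Conclusion.** The concern holds. A stated screen fails one of its two stated purposes, and no other named question fills the gap. It is a modest gap in safety ascertainment that should be corrected; it does not threaten the trial, and the responder and seizure-frequency analyses are untouched.

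Its size is about 50 on-drug calls without a low-mood question, or 100 to 150 calls once the baseline phase and the longest cycles are counted. These counts rest on 30-day spacing and full enrollment of 50. They measure contacts. No number of missed cases can be derived from the documents, and none is claimed.

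**What to change.** Replace the sentence in item 2 with wording such as: *At every telephone call, in both the baseline and treatment phases, we will ask about suicidality and ask two standard questions, one on low mood and one on loss of interest.* The exact questions, and what counts as a positive answer, should be written down before the first call.

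- Record both answers in REDCap.
- The coordinator reports a positive or changed answer to the investigator by the route already used for a change in the C-SSRS.
- The investigator handles a new or worse symptom as an adverse event on the existing severity scale.
- A suicidal answer follows the existing suicidality plan.

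The baseline calls give a pre-drug reference, though a thin one at about one call per woman. Asking the same questions at enrollment and visits is optional. No new visit, call, stopping rule or outcome is needed.

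**Cost.** Entries: 2 × 100 = 200 to 2 × 150 = 300. The times below rest on assumptions: 1 minute per call to ask, 10% to 30% of calls positive, and 10 minutes of follow-up for each positive call.
- Asking: 100 to 150 minutes, or 1.7 to 2.5 hours.
- Follow-up: 100 × 0.10 × 10 = 100 minutes (1.7 hours) to 150 × 0.30 × 10 = 450 minutes (7.5 hours).
- Total: 100 + 100 = 200 minutes (3.3 hours) to 150 + 450 = 600 minutes (10 hours).

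The 10 minutes does not separately itemize IRB reporting of any extra adverse events, so the true figure could be somewhat higher.

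### No C-SSRS is scheduled while study drug is being taken, so the step that alerts the PI to a change in the scale cannot operate during dosing

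*Protocol*

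**What the plan says.** The Protocol's Safety Measures section, item 2, calls for a C-SSRS at enrollment and a check for change in the scale at each follow-up visit. Its suicidality plan has two parts. Item a covers the scale: "C-SSRS will be performed at each visit by study coordinator. Study coordinator to contact PI if there is a change in the C-SSRS". Item b covers the response to suicidal ideation or behavior: emergency referral, a hotline number, and then "Will also discontinue enrollment in trial and study drug". Item b names no instrument.

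Telephone contacts are handled differently: "During each telephone call, we will screen for depressive symptoms and suicidality by asking patients if they are suicidal".

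The visit schedule is in the Data Collection entry that follows Statistical Analysis: "Subjects will be seen in the clinical trial clinic for three separate visits". Their timing is "at enrollment and then also after the completion of baseline (first 2 months of charting) and treatment phases (second 2 months of charting". The same entry makes telephone calls monthly and uses them to check charting and treatment compliance and to look for adverse effects.

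On the start of dosing, Study Design says: "Subjects will chart menses and seizures for a 2 month baseline period and then be randomized into 2 parallel arms". On its length, Study Drug Regimens says: "This treatment phase will last for two menstrual cycles". The SAP says nothing about the C-SSRS.

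**The concern.** Read alone, the Safety Measures section suggests that a structured suicidality scale is repeated through the trial and that a worsening score reaches the PI in time to matter. Read with the visit schedule, it does not work that way. The first C-SSRS that could show a change arising on drug is given once the treatment phase is complete, when no planned dosing remains.

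At stake is how a change would be noticed while a woman is taking perampanel. The study is unblinded and has no internal data safety monitoring board; the PI and the coordinator run safety monitoring themselves. The structured instrument chosen for the purpose is absent from the one period in which its result could affect continued dosing, and a single question by telephone takes its place.

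**Working it through.** The check is a count on a timeline.

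**Inputs**
- Visits: three, at enrollment, after baseline and after treatment (Data Collection).
- C-SSRS: at visits (Safety Measures, item 2). Calls use a direct question instead.
- Dosing: starts after the 2-month baseline (Study Design) and lasts two menstrual cycles (Study Drug Regimens).
- Eligible cycle length: 21 to 35 days (Inclusion Criteria, item 3).
- Supply calculation: 60 days per woman (Study Drug Requested Per Patient).
- Calls: monthly (Data Collection).

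**Reproducing the plan's figures.** Visits: 1 (enrollment) + 1 (after baseline) + 1 (after treatment) = 3, as stated. Supply for the first group: 25 × 60 = 1500 tablets, as stated, so 60 days is the planned dosing length.

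**Placing each C-SSRS against dosing**
- Visit 1, month 0: no drug yet.
- Visit 2, about month 2: baseline complete, before the first dose.
- Visit 3, about month 4: treatment phase complete.

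Scheduled C-SSRS within dosing: 0 of 3 per woman. For 50 women that is 0 of 50 × 3 = 150.

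**Gap between the pre-dose and post-treatment scale**
- Shortest eligible cycles: 2 × 21 = 42 days.
- Planned supply: 60 days.
- Longest eligible cycles: 2 × 35 = 70 days.

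These figures place visit 2 at the start of dosing and visit 3 at its end. Any delay at either visit lengthens the gap.

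**Telephone screens within dosing.** The call days are not given, so I assume one every 30 days from the start of treatment.
- 42 days: one call (day 30).
- 60 days: one call strictly inside (day 30), or two if the call on the final day (day 60) is counted.
- 70 days: two calls (days 30 and 60).

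**What each safety step can do during dosing**
- Item a needs a C-SSRS result. None is scheduled in the interval, so it cannot act.
- Item b needs suicidal ideation or behavior, from any source. A positive answer on a call meets it, so it can act at one or two scheduled contacts, and at any time if a woman reports a problem herself.

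**The case against.** The strongest reply is that the two sections do not conflict. The plan gives the scale at visits and a direct question at calls, and the schedule follows that. On this view, using the full scale at calls is a preference about how intensive monitoring should be. It is true that neither statement falsifies the other. What remains is that item a is written as a working alert, and on this schedule it cannot alert anyone during dosing.

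A reader might go further and infer that the rule stopping study drug never operates while drug is taken. The documents do not support that. Item b is not conditional on item a or on a C-SSRS result, and the monthly calls ask about suicidality during treatment. The same calls also ask about aggression and harm to others, with their own steps for stopping drug. That is not a suicidality screen, but it shows that the calls are genuine safety contacts.

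A reader might also infer that the C-SSRS gives no information about the treatment period. That too goes beyond the text. The third assessment may pick up events during treatment in retrospect. The Protocol states neither its recall period nor the interval from last dose to visit 3, so the point cannot be settled either way.

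**Conclusion.** The narrow point stands. The scale and its alert step are absent during dosing for every woman in both arms. The stopping rule remains live, but scheduled detection feeding it depends on one unstructured question, asked once or twice.

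The conclusion assumes that there are no unscheduled visits and no study drug after the treatment phase; the Protocol describes neither. It also assumes that visit 2 comes before the first dose. The zero count does not depend on cycle length or call spacing; only the length of the gap and the number of calls do.

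I would rate this as a cheap improvement to safety monitoring, not as something that must be fixed before the trial can run.

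**What to change.** Reconcile the suicidality plan in Safety Measures with the visit schedule in Data Collection, so that the check for a change in the C-SSRS has at least one assessment point within the treatment phase. One contact already in the plan is the monthly treatment-phase call, with the existing step of informing the PI. Whether to use that call or another contact is for the investigator to decide. Item b can stay as written.

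The cost is about one sentence in the Protocol and one repeated REDCap form. If the call is used, it becomes slightly longer.
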